6. STUDY SUBJECTS

6.1 INCLUSION CRITERIA

1. ≥ 18 years of age
2. Structural heart disease (post-MI, dilated cardiomyopathy, sarcoid myopathy, hypertrophic cardiomyopathy, etc.)
3. Planned for ICD implantation for:
 - i. Secondary prevention (e.g.: VT/VF arrest, sustained VT, syncope/inducible VT)
 - ii. Primary prevention + inducible MMVT during induction via ICD lead testing
 - iii. Primary prevention + fragmented QRS complex on 12-lead ECG
4. Accessibility of renal vasculature (determined by renal angiography)
5. Ability to understand the requirements of the study
6. Willingness to adhere to study restrictions and comply with all post-procedural follow-up requirements

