9.4.5 EVENT RECORDING

The following adverse events will be captured throughout the period of trial participation:

- Protocol-defined (as described above)
- Serious unanticipated events (serious “*Other*” adverse events)

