The primary safety objective is to demonstrate that the incidence of serious adverse events (events that cause clinically relevant changes in patient's health, or any event that is life-threatening, results in a fatality, results in permanent disability, requires hospitalization, or prolongs an existing hospital stay) is not increased with the use of the ICD + RSDN compared to ICD alone.

10.5 SECONDARY ENDPOINTS:

The following secondary endpoints will be assessed:

- Appropriate ICD therapy assessed in the full intention-to-treat patient cohort
- Inappropriate ICD therapy
- Number of Hospitalizations for Cardiovascular Causes.
- Total VT burden (Number of episodes).
- All-Cause Mortality.
- The occurrence of ICD storm, defined as ≥ 3 appropriate shock therapies within 24 hours.
- Differences in BUN/creatinine measurements.
- Procedure related adverse events including, but not limited to hematomas, pseudoaneurysms and renal artery stenosis.
- Development of orthostatic hypotension
- 30-day Major Complication Rate defined as death, stroke, MI or any other serious adverse events related to the treatment or procedure within the first 30 days or through hospital discharge (whichever is longer).

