10.8 STATISTICAL ANALYSIS

The primary analysis will be an intent-to-treat analysis that will include all randomized participants regardless of treatment actually received or follow-up schedule.

Point Estimation and Interval Estimation: We will report maximum likelihood estimates for point estimation. For routine reporting, two-sided 95% confidence intervals for all parameters will be prepared.

Disposition of Participants and Baseline Comparisons: Summaries of all participants randomized and the number who complete visits at 30-days, and every 6 months after the day of randomization will be provided for each treatment group. The treatment groups will be compared at baseline with respect to demographics, baseline measurements related to efficacy and baseline measurements related to safety.

Univariate Analysis: All outcome measures will be described in a univariate analysis. For continuous variables means and standard deviations will be calculated. For discrete and dichotomous variables we will use contingency tables.

Analysis of Primary Endpoint: The primary endpoint of this study is defined time to first event requiring any ICD therapy (appropriate or inappropriate) or Incessant VT (VT occurring below the ICD rate cut-off); this will be assessed in the on-treatment patient cohort. An event requiring ICD therapy is defined as an anti-tachycardia pacing (ATP) or shock therapy. Time to event will be estimated using Kaplan-Meier curves. Survival time will be defined as the time (in months) between randomization and the occurrence of first ICD therapy. To compare the ICD+ RSDN arm with the ICD alone arm we will use a stratified log-rank statistic (using the stratification variables from the randomization procedure). A Cox proportional hazards model with treatment and other important prognostic factors as covariates will be used for the multivariate analysis of the times to first ICD therapy. Risk ratios and their 95% confidence intervals will be computed. Patients will be included in the analysis as censored if they are alive and free of ICD events at the end of the 18-month follow-up period. Although we do not anticipate interactions between treatment and stratification factors, formal tests for interactions will be assessed using proportional hazards models. A formal test of proportional hazards will assess the significance of

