the interaction between the indicator for treatment group and log (t) in a Cox proportional hazards regression model that also includes the main effect for the randomization group. The final analysis will be based on a two tailed 0.0492 level test.

Analysis of Secondary End-points: All continuous variables will be analyzed using mixed effects models (Bagiella et al. 2000; Diggle et al. 1994; Laird and Ware 1982). Log-transformations will be used, if necessary to normalize the variables or stabilize the variance. For binary and discrete outcomes we will use generalized estimating equations (GEE) (Liang and Zeger 1986; Miller et al. 1993; Zeger and Liang 1986) to fit logistic or log-linear models that account for the dependency of the repeated measures.

Missing Data: For participants who withdraw consent to participate we will use all the information available up to the time of withdrawal. For the purpose of the primary analysis these patients will be censored at the time of withdrawal if they have not experienced the primary event. For all other variables, if the data are missing at random (MAR), that is, the probability of being missing depends only on observed values (Little and Rubin 1987), then likelihood-based methods such as mixed-effects models will be used for analysis without bias. If the fraction of missing data is small we expect that even non-ignorability can have only little effect on the final estimates. If the extent of missingness is large compared to the effect size, we will use the multiple imputation procedure proposed by Rubin (1997) and Little (1996).

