10.9 PRIMARY SAFETY ANALYSIS

The primary assessment of safety will be based on the incidence of all serious adverse events over the total duration of study follow-up. The between group comparisons of incidence of serious adverse events will be estimated using the incidence rate ratio and corresponding 95% confidence intervals based on Poisson regression.

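### Section 10.9 fixes neither how serious adverse events are counted nor a variance for within-patient dependence, so its 95% Poisson interval can be too narrow or too wide

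*Combined protocol and SAP*

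**What the plan says.** Section 10.9 is two sentences long. The first sets the measure: "The primary assessment of safety will be based on the incidence of all serious adverse events over the total duration of study follow-up". The second says that the comparison between arms will be "estimated using the incidence rate ratio and corresponding 95% confidence intervals based on Poisson regression".

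Neither sentence says whether repeat SAEs in one patient enter the count, what time at risk each patient contributes, or which variance estimator gives the interval.

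Other sections add the following:

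- **10.8, point and interval estimation:** "We will report maximum likelihood estimates for point estimation", with two-sided 95% intervals for routine reporting. No variance estimator is named.
- **10.8, secondary endpoints:** binary and discrete outcomes use generalized estimating equations "to fit logistic or log-linear models that account for the dependency of the repeated measures". This paragraph does not extend to 10.9.
- **9.4.5:** "The following adverse events will be captured throughout the period of trial participation", followed by the types of event recorded.
- **10.4:** the SAE definition includes events that require or prolong a hospital stay, so one patient can have several.
- **9.2.1 and 10.6:** follow-up runs to at most 36 months, with a minimum of 18. The Design row of the Protocol Summary mentions 12 months.

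**The concern.** A Poisson model takes the variance of a count to equal its mean. SAE counts per patient usually vary more than that, because some patients are sicker and have several events. The population here is mixed. Section 6.1 admits patients under "Secondary prevention (e.g.: VT/VF arrest, sustained VT, syncope/inducible VT" and also under "Primary prevention + fragmented QRS complex on 12-lead ECG", with any structural heart disease. If every event is treated as independent, the standard error is then too small.

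The opposite error arises if *incidence* is read as the proportion of patients with at least one SAE. A Poisson model fitted to yes/no data overstates the variance, and the interval is too wide.

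Two analysts could therefore both follow 10.9 and report different primary safety intervals. An interval that is too narrow would signal a difference too often when there is none. It would also place the upper bound on a possible SAE increase too low, and that bound is the figure that speaks to the objective in 10.4.

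**Working it through.** The documents give no SAE rate, dispersion or safety precision, so there is no figure of the plan's own to reproduce.

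**Inputs.** 231 patients per arm (Protocol Summary). Follow-up *t* taken as uniform over 18-36 months (range from 9.2.1 and 10.6; uniformity assumed). Assumed: a true rate ratio of 1, a mean of *m* = 0.25 to 1.5 SAEs per patient, and gamma-distributed patient risk with mean 1 and variance *v* (the frailty variance) from 0 to 1.

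**Case A: repeats count.**

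- Model-based SE of the log rate ratio = √(2/(231*m*)).
- True SE = model-based SE × √D, with D = 1 + *v* × *m* × E[t²]/E[t]². For uniform 18-36 months, E[t²]/E[t]² = (27² + 18²/12)/27² = 756/729 = 1.037.
- Actual coverage = 2Φ(1.96/√D) − 1.

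| *v* | *m* = 0.25 | *m* = 0.5 | *m* = 1.0 | *m* = 1.5 |
|---|---|---|---|---|
| 0 | 95.0% | 95.0% | 95.0% | 95.0% |
| 0.125 | 94.6% | 94.2% | 93.5% | 92.7% |
| 0.25 | 94.2% | 93.5% | 91.9% | 90.4% |
| 0.5 | 93.5% | 91.9% | 88.8% | 85.8% |
| 1 | 91.9% | 88.8% | 83.0% | 78.0% |

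Simulation with 8,000 trials per setting agrees to within one percentage point (for example 77.2% to 92.2% at *v* = 1). At *v* = 1 the simulated lower limit exceeded 1 in 3.8%, 5.7%, 8.3% and 11.7% of trials across the four means, against a nominal 2.5%. On the same data, a robust variance clustered on patient gave coverage of 94-95% in every setting.

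**Upper bound at an observed ratio of 1 and *m* = 1.0.** The model-based SE is √(2/231) = 0.0930, so the bound is exp(1.96 × 0.0930) = 1.20. At *v* = 0.25, D = 1.259 and the true SE is 0.1044, giving 1.23. At *v* = 1, D = 2.037 and the true SE is 0.1328, giving 1.30.

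**Case B: each patient scored once, yes or no.** With a proportion *p* having an SAE, the model-based SE is √(2/(231*p*)) and the true SE is √(2(1−*p*)/(231*p*)). The interval is too wide on the log scale by a factor 1/√(1−*p*). That is 1.12 at *p* = 0.20 (coverage 97.2%) and 1.41 at *p* = 0.50 (coverage 99.4%).

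**Case C: first SAE only, with time at risk ending at that event.** Simulated coverage is about 93-95%, close to nominal.

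**How much variance the mix of indications could explain.** For two groups whose rates differ *k*-fold, the frailty variance cannot exceed (*k*−1)²/(4*k*). A twofold difference gives at most 1/8 = 0.125, and a threefold difference at most 4/12 = 0.33. A variance of 1 needs (*k*−1)² = 4*k*, so *k* is about 5.8.

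**The case against.** The strongest reply is that nothing in 10.9 is wrong as written. Poisson regression does not exclude a robust variance, no test, margin or decision rule is attached to the interval, and early stopping under 9.3.1 runs through the DSMB and its 15% threshold, neither of which uses it. That stands, and it limits the consequence to the final safety estimate.

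The documents also do not support the larger losses of coverage as expected values. They give no SAE rates by indication. A twofold or threefold difference between indications yields a variance of at most 0.125 or 0.33, where the loss is modest. Other unmeasured differences between patients are plausible but unquantified. Shorter follow-up, as in the 12 months of the Protocol Summary, would lower the counts per patient and the loss with them.

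A reader might infer more than the text allows in four places:

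- *That the interval is certainly too narrow.* It is not, because the direction depends on a counting rule that 10.9 leaves open.
- *That 9.4.5 settles that repeats count.* It says which events are recorded and for how long, not how they enter the comparison.
- *That 10.8 commits the trial to a model-based variance.* Its maximum likelihood sentence concerns point estimates.
- *That a secondary count such as "Number of Hospitalizations for Cardiovascular Causes" (10.5) is protected while the primary safety count is not.* The GEE paragraph probably covers it, but 10.8 does not say how that count is structured.

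What remains after these concessions is that no section supplies the counting rule or a patient-level variance for the primary safety comparison.

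**Conclusion.** The point holds as a two-way ambiguity in the primary safety analysis that should be closed before the data are analysed. On the natural reading (all events, a rate ratio, total follow-up) the ordinary Poisson interval is too narrow whenever patients differ in SAE risk. Over 0.25 to 1.5 SAEs per patient, coverage is about 93-95% at frailty variance 0.125, 90-95% at 0.25, 86-94% at 0.5 and 77-92% at 1. With equal risks it is correct. On the yes/no reading it is too wide, at about 97-99% coverage.

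These sizes rest on assumed rates, assumed gamma frailty and 18-36 months of follow-up. They show what could happen and do not predict this trial's result. The efficacy analysis is not affected. The absence of a margin for the objective in 10.4 is a separate issue; it neither supports this point nor is resolved by it.

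**What to change.** Add to 10.9: all SAEs, including repeat events in the same patient, are counted from randomisation to death, withdrawal or end of follow-up; the rate ratio and its 95% interval come from Poisson regression with log follow-up time as offset and a robust variance clustered on patient. Negative binomial regression with the same offset may be named as a sensitivity analysis. The objective in 10.4 need not be reworded for this purpose.

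The cost is a few lines of SAP text and one variance option on data already collected. The downside is a wider interval when patients differ in risk. At 1.0 SAE per patient the standard error rises by about 12% at variance 0.25 (√1.259 = 1.12) and 43% at variance 1 (√2.037 = 1.43). When patients share one risk there is on average no widening.

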11.0 STUDY MANAGEMENT

11.1 STUDY DATA COLLECTION AND PROCESSING

The Case Report Form (CRF) is an integral part of the study and subsequent reports. The CRF must be used to capture all study data recorded in the patient's medical record. The CRF must be kept current to reflect patient status during the course of the study. Patients will be identified by a 5 digit number and their initials. The investigator must keep a separate log of patient names and medical record numbers (or other personal identifiers) for their own reference. All study-related documents (CRFs, source medical records, regulatory binder) must be kept in a secure, locked environment with access limited to study personnel only.

The PI is responsible for ensuring the following at his/her site: 1) adherence to the protocol; 2) verifying adherence to local regulations on the conduct of clinical research; and 3) ensuring completeness, accuracy, and consistency of the data entered in the CRF.

Final CRFs in human readable format must be reviewed and verified for accuracy by the study site Principal Investigator and signed-off. A copy of the final CRF will remain at the investigator's site at the completion of the study.

The CRF numbering convention is as follows:

01 - 2 3 4 A -B -A
01 : Site # must be 2 digits (use leading zero) --- (sites 01-10)

2 3 4 : patient screening/enrollment # (001 – 500) — must be 3 digits

A-B-A: Patient initials (if no middle initial, use dash)
Total 5 digits and initials for enrolled patients.

11.2 CONFIDENTIALITY

Patient information will be kept confidential and managed according to the 1996 HIPAA guidelines. All patient information will be de-identified and stored in a secure, locked environment. Each patient will be given a unique subject number and will be identified by this number and their initials. All data used in the analysis and reporting of this evaluation will be without identifiable reference to the patient. Data relating to the study might be made available to third parties (for example in case of an audit performed by regulatory authorities) provided the data are treated confidential and that the patient's privacy is protected.

11.3 DEVIATIONS FROM PROTOCOL

The investigator will not deviate from the protocol except in medical emergencies or in unforeseen, isolated instances where minor changes are made that will not increase the patient's risk or affect the validity of the trial. In medical emergencies, prior approval for protocol deviations will not be required, but the IRB/EC must be notified within five days of the incident.

11.4 WITHDRAWAL OF SUBJECTS

A subject may withdraw from the study at any time should they choose to do so. Additionally, subjects may be withdrawn by the investigator if deemed appropriate due to safety or compliance issues.

11.5 ECONOMIC IMPACT ON SUBJECTS

The catheter-based renal sympathetic denervation procedure is part of a research study and is investigational. The cost of the renal sympathetic denervation procedure and follow-up will be the responsibility of the subject or the subject's insurance carrier. No payment will be made to the subject for taking part in this study.

12.0 ETHICAL AND REGULATORY CONSIDERATIONS

12.1 RISK TO SUBJECTS:

Although it is unlikely, it is possible there may be loss of confidentiality. This is a typical risk of any research study. Stenosis, dissection, and groin complications are possible clinical risks however they are not anticipated risks in this trial.

12.2 POTENTIAL BENEFITS TO SUBJECTS:

After undergoing RSDN, patients may experience less episodes of VT requiring ATP or shocks a result of the expected reduction in whole body norepinephrine spillover and sympathetic nerve activity.

12.3 ROLE OF THE DATA COORDINATING CENTER

As principal investigator and study sponsor of this clinical study, [name] assumes the overall responsibility for the conduct of the study, including assurance that the study meets

national and institutional guidelines for study conduct. In this study, [name] will have certain direct responsibilities and will delegate other responsibilities to his staff at the Data Coordinating Center at Icahn School of Medicine at Mount Sinai. Together, the Data Coordinating Center will: 1) ensure adherence to the national and institutional regulations; 2) develop and distribute protocols and case report forms; 3) coordinate data organization; 4) perform statistical analyses.

12.4 ONSITE MONITORING

The primary objectives of the DCC in monitoring clinical sites are to educate, support, identify and resolve issues related to the clinical trial. The monitors will discuss the protocol in detail, and clarify any areas of uncertainty. At initiation of the study, the monitors will conduct a tutorial on the EDC system. The coordinators will practice entering data so that the monitors can confirm that the coordinators are proficient in all aspects of data entry, query response, and communication with the data management team.

The DCC will employ a risk-based approach to monitoring for this study. This will be accomplished via centralized or remote monitoring of data via the EDC with a focus on safety, study endpoints, data completion and data outliers. The DCC will also centrally monitor study logs including the Informed Consent Log, the Protocol Violation/Deviation Log and the Serious Adverse Event Log periodically to ensure that the sites are adhering to the study protocol and procedures. The DCC will generate performance metrics to analyze site characteristics such as recruitment rates and timeliness of data entry. This will allow the DCC to identify trends across sites and to address low-performing sites appropriately.

The DCC will also conduct one on-site monitoring visit each year for every clinical site for the duration of the study. In addition, interim monitoring will be conducted on an ongoing basis using the EDC system. During the annual on-site monitoring visits, the monitor will collect copies of any source documents (de-identified) for all deaths and AEs. Prior to each EAC meeting copies of any source documents (de-identified) requested by the DCC must be sent via FedEx or secure fax line to the DCC.

The monitors will review the source documents to determine whether the data reported in the EDC system are complete and accurate. They will also verify that all serious and protocol-defined adverse events exist on the source documents, are consistent with the protocol and are documented in the appropriate format. Source documents include medical charts, initial hospital admission reports, operative procedure records, discharge and re-admission reports, consult notes, radiology reports, lab reports, clinic records, and other study-related notes. The study monitors reserve the right to copy de-identified records in support of all adverse events and outcomes.

The monitors will also confirm that the regulatory (administrative) binder is complete and that all associated documents are up to date. The regulatory binder should include all revisions of the protocol and informed consent, IRB roster, IRB approvals for all of the above documents, IRB correspondence, investigator's agreements, CVs of all study personnel, institutional HIPAA certificates, monitor site visit log, telephone contact log, a study device log and correspondence with the DCC.

If a problem is identified during the visit (i.e., poor communication with the DCC, inadequate or insufficient staff to conduct the study, missing study documents, etc.), then the monitor will assist the site in resolving the issue. Some issues may require input from the Steering Committee or the Principal Investigator, as well as the sponsor.

The combination of yearly on-site monitoring and ongoing monitoring using the EDC system that includes instantaneous electronic validation, and visual cross-validation to detect complex errors, it is anticipated that the best possible quality and most complete data will be collected.

The monitor will verify a minimum of the following variables for all patients: initials, date of birth, sex, signed informed consent, eligibility criteria, date of randomization, anticoagulation, serious and protocol-defined adverse events, and mortality. These data will be 100% source data verified. All other data collection will be monitored as indicated by the data completeness and accuracy at each clinical site.

12.5 MAINTAINING RECORDS (21 CFR 812. 140 (B))

The Data Coordinating Center will maintain copies of correspondence, data, shipment of devices, adverse device effects and other records related to the clinical trial.

12.6 SITE RECORD RETENTION POLICY

All clinical sites will maintain study records for two years after research termination.

12.7 INSTITUTIONAL REVIEW BOARD (IRB) / ETHICS COMMITTEE (EC) INFORMATION

This protocol and the informed consent must be reviewed and approved by the appropriate IRB/EC where the trial is to be conducted before enrollment of patients. Changes to the protocol that may increase the risk or present new risks to the patient, or may adversely affect the validity of the trial, must be approved in writing by the IRB/EC before the change is made.

The study site Principal Investigator(s) is responsible for submitting and obtaining initial and continuing review (at intervals not greater than once a year) of the trial by their IRB/EC.

